## II-5 Restorative procedures:

Each included patient with the already prepared cavities will receive two different types of restorations. where one of them will be restored with light cured nano hybrid RBC (Filtek™ Z250, 3M ESPE St.Paul,M,USA) (M1) meanwhile, the second cavity will be restored with self-cure bioactive RBC (Stela, SDI, Australia) (M2).

A sectional matrix system will be used to achieve proper proximal contour and anatomically correct contact with the adjacent tooth. Then, the restorative procedure of each cavity will be carried out according to the manufacturer's recommendations of each tested restoration. Before restoration each cavity will be carefully cleaned with copious air water spray before being dried. Restoration of (M1) group will be performed through selective etching of the prepared cavity enamel surface using 37% phosphoric acid gel (Meta Biomed, Korea) for 15 seconds. This will be followed by rinsing with water for 15 seconds and gentle air drying for 5 seconds, leaving the cavity slightly moist. After that, single layer of a universal adhesive bonding agent (Bisco, INC Schaumburg, IL, USA) will be applied to the prepared cavity walls and floor using disposable adhesive micro brush. The adhesive will be subsequently cured for 20 seconds using LED light curing unit (Elipar S10, 3M ESPE, St Paul, Minnesota, USA) with an intensity of 1200 mW/cm^2. The nano hybrid RBC (Filtek™ Z250) will be incrementally applied, and light cured according to manufacturer instructions. Finally, finishing and polishing of the restoration using one-step polishing system (Dimanto, Voco, Germany). Then, checking of occlusion and proximal contacts will be done.

Restoration of (M2) group will be performed through conditioning of cavities with a specialized primer (STELA primer, SDI, Australia) according to manufacturer instructions. Then, a self cured bioactive RBC (STELA, SDI, Australia) will be placed in a single increment and allowed to self-cure according to manufacturer instructions. Then, finishing and polishing of the restoration, checking the occlusion and proximal contacts will be done as mentioned before.

#### **II-6- Evaluation of the wear resistance:**

A digital impression will be taken immediately after restoration (T0) using an intraoral scanner (Helios 600 intraoral scanner, Eighteeth, Changzhou, China). To ensure optimal performance and accuracy, the scanner underwent regular calibration before scanning each patient, following the manufacturer's recommendations. During the scanning procedure, the device will be positioned at a 90° angle for the occlusal surface and at 45° angles for both buccal and lingual surfaces. Later on, each restoration will be examined at standardized follow-up periods (Table 2 and 3); six months (T1), twelve months (T2), eighteen months (T3) and twenty-four months (T4). The 3D impressions will be analyzed using a software (Geomagic software, 3D Systems Inc., USA) program and the impressions of each two consultative visits will be superimposed to determine the wear volume loss (mm^3). (Bronkhorst et al, 2022)

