#### Methodology:

Twelve healthy patients with 24 carious molar teeth will be selected where each patient should have two ocluso- mesial cavities. Standardized

occluso- mesial cavities will be prepared for all the selected teeth, for each patient the first tooth will be restored with conventional nanohybrid RBC (M1). Meanwhile, the second tooth will be restored by self-cure bioactive RBC (M2). Then, wear resistance will be evaluated by intraoral scanner immediately after restoration (T0), six months later (T1), after 12 months (T2), 18 months (T3) and 24 months (T4). Software analysis will be done by superimposing the 3D digital impression and evaluate the restoration wear by calculating the 3D volume loss.

Also, bioactivity of the restoration will be measured by measuring the mineral density beneath the restoration. Digital radiographic images will be taken for the restoration by parallel technique and grey scale of the pixels under restoration will be measured by software immediately after restoration (D0), one month later (D1) and after 3 months (D2).

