The wear of dental restorations using an intraoral scanner and its correlation with visual assessment was evaluated prospectively. Thirty six patients were followed-up by intraoral optical impression and visual assessment over three appointments over 12 months, where T0 is the base line, T6 after 6 months, and T12 after 12 months. The results

showed that: According to the visual indices, all restorations in this study were clinically healthy. However, in the digital measurement of wear, 94.74% and 94.44% of the restorations during the T0-T6 and T6-T12 observation periods, respectively, showed deterioration greater than 41 microns. Discordant results were obtained in the correlation analysis. In T0-T6, the results were not considered statistically significant; however, the results obtained during T6-T12 showed a correlation. They concluded that wear of dental materials as observed by the human eye did not agree with that observed by intraoral scanning. The scanner effectively measures wear, detecting details that are beyond the capability of the human eye and conventional photographs (*Urcelay et al, 2025*).

Digital and conventional methods of wear analysis using two hybrid ceramic materials were compared. Disc-shaped samples (2 mm thick and 10 mm in diameter) were prepared from Vita Enamic and Cerasmart materials and subjected to chewing simulation. Wear evaluation was conducted using two approaches: conventional weight loss assessment before and after simulation, and digital analysis via Geomagic software by superimposing 3D scan images taken with intraoral scanner. The results revealed a positive correlation between the conventional and digital measurement methods. Statistically significant differences were observed between the two materials in terms of wear behavior. Vita Enamic demonstrated considerably more wear than Cerasmart 270 across both evaluation techniques. They concluded that both weight-based and digitally calculated volume loss methods are reliable for wear assessment, with Cerasmart 270 showing

superior resistance to wear compared to Vita Enamic (ElSharouny et al, 2025).

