### **3. Research Q (RQ):**

What is the difference between self cured bioactive and light cured nanohybrid (RBCs) regarding wear resistance and bioactivity after two years of clinical performance?

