#### **II-7- Assessment of the bioactivity:**

Bioactivity of each examined restoration will be determined by the evaluation of mineral density beneath the tested materials. Immediately after restoration (D0), an image plate digital sensor (Xios XG Supreme, Dentsply Sirona, UK) will be used for transmitting the radiographic

image of the selected tooth to the computer. A posterior parallel kit will be used for image standardization. Later, each restoration will be examined at standardized follow-up periods; one month (D1) and three months (D2) (Table 4 and 5). The image plate will be inserted at one end of the parallel kit, while the other end was connected to the x-ray cone. All the radiographs will be evaluated for the outcome by a software (ImageJ software, NIH, USA). The assessment of mineral density will be done by the software through performing the following measurements: in each image a line will be drawn along the CEJ to act as a reference, while another parallel line will be drawn at the bottom of the cavity. The distance between both lines will be standardized for each tooth by measuring the length of a vertical line connecting them. The length of the line centralized at the bottom of the cavity will be determined in pixels directly via the previously mentioned software. Such length will be fixed for each sample throughout assessment intervals. Three points on this line (at its start, middle and end) will be determined. The mineral density value at each of these points will be identified by taking the corresponding three readings from the software and recording them to calculate the average value. The mineral density mean value will be calculated from the software (Ibrahim et al, 2016).

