**Table 2: Variables of the wear resistance test and levels of investigations:**

Variable	Level	Referred to
Type of material (M).	M1	Light cured nanohybrid RBC.

Time of follow-up (T).	M2	Self-cured bioactive RBC.
	T0	Immediately after restoration.
	T1	After six months.
	T2	After twelve months.
	T3	After eighteen months.
	T4	After twenty-four months.

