### Statistical analysis:

All collected data will be calculated, tabulated, and statistically analyzed using suitable statistical tests as follows: **A normality test:** will be done to check normal distribution for data by Shapiro-Wilk test. **Descriptive statistics:** will be calculated in the form of mean  $\pm$  standard deviation (SD), range (Max-Min). Qualitative data will be presenting as (%) frequencies (n) and percentages. **T- test or Mann-Whitney test**

**(According to the types of data).** Independent Student's T-test or Mann-Whitney will be performed for pair wise comparison between groups in each time at P value < 0.05. **The Chi-square test** will be used to test significance of association between categorical variables. **Pearson's correlation coefficient:** will be used for estimating the relationship between quantitative variables. **P<0.05** is considered significant. Statistical analysis will be performed using the computer program SPSS software for windows version 26.0 (statistical package for social science, ARMONK, NY: IBM Corp).

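### Section II-6 does not name T0 as the reference scan, so on its most natural reading the 24-month wear value is the month 18–24 loss, not the two-year loss

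*Protocol*

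**What the plan says.** Section 3 (Research Q) asks how the two materials differ "regarding wear resistance and bioactivity after two years of clinical performance".

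Section II-6 sets out the wear measurement. It begins with the baseline: "A digital impression will be taken immediately after restoration (T0) using an intraoral scanner". Follow-up scans come at 6, 12, 18 and 24 months (T1 to T4). The rule for turning scans into wear is that the "impressions of each two consultative visits will be superimposed to determine the wear volume loss", in cubic millimetres.

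Other parts of the protocol touch on the same value:

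- The abstract (Methodology) describes "superimposing the 3D digital impression and evaluate the restoration wear by calculating the 3D volume loss".
- Table 2 defines T4 only as "After twenty-four months".
- Table 3 crosses material with T0 to T4 and does not say what quantity each cell holds.
- The statistical analysis section plans a "pair wise comparison between groups in each time at P value < 0.05", so a comparison at T4 is intended.

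**The concern.** Wear from scans is always a difference between two scans, so a wear value labelled T4 means nothing until its reference scan is named. Section II-6 is the only place that states a pairing rule, and the key word in that rule does not fit its context. The obvious repair, consecutive, gives a chain of six-month increments. The headline comparison at 24 months would then describe only the last half-year of a two-year trial.

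Two things are at stake. An analyst who follows the rule on that reading would report a T4 result that does not answer the trial's own question. An analyst who reads it differently would report another quantity under the same label, and the choice could be made after the data are seen.

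**Working it through.** The protocol gives no figure of its own for this point, so the check sets the possible readings beside the text and counts.

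**Inputs.** Five scans per tooth, at months 0, 6, 12, 18 and 24 (section II-6). Twelve patients with two teeth each (abstract). A between-material comparison at each time (statistical analysis section). A two-year horizon (section 3).

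**What each reading makes of T4.**

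| Reading of the pairing rule | Pairs formed | Value compared at T4 | Answers the two-year question? |
|---|---|---|---|
| Consecutive visits | T0–T1, T1–T2, T2–T3, T3–T4 | loss over months 18–24 | No |
| Each follow-up against baseline | T0–T1, T0–T2, T0–T3, T0–T4 | loss over months 0–24 | Yes |
| Any two visits | 5 × 4 / 2 = 10 pairs | not assigned | Only if T0–T4 is chosen |

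**Share of follow-up under the consecutive reading.** 24 − 18 = 6 months, and 6 / 24 = 25%.

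**Share of the two-year loss (assumption).** The protocol gives no wear rates. Suppose that each six-month loss is *r* times the one before. The last interval then holds r³ / (1 + r + r² + r³) of the total:

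- r = 1 (constant wear): 1 / 4 = 25%
- r = 0.75: 0.422 / 2.734 = 15%
- r = 0.5: 0.125 / 1.875 = 7%

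If wear speeds up, the share exceeds 25%. These values show only that the last increment cannot stand in for the total.

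**Does another section settle the reading?** The abstract mentions superimposition without a reference scan. Table 2 gives only the timing of T4. Table 3 includes cells at T0, where a loss would be zero by definition (baseline reading) or would not exist (consecutive reading), so the table does not define its entries either. The statistical section takes the value at each time as given. No section plans to sum the increments.

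**Why wear carries the two-year question.** Mineral density is measured only up to three months (section II-7). Of the two outcomes named in section 3, wear alone has data at two years.

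**Workload.** 12 × 2 = 24 teeth. Four superimpositions per tooth, consecutive or against T0: 24 × 4 = 96. The intervals T1–T2, T2–T3 and T3–T4 measured as well: 24 × 3 = 72 more.

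**The case against.** The strongest reply is that section II-6 opens with the T0 scan and then lists T1 to T4 as follow-up, so pairing each visit with baseline is a possible reading. On that reading the planned T4 comparison does test the two-year loss. This stands. A reader might infer that the protocol can never deliver a two-year comparison, and the documents do not support that. They also do not say that the baseline reading applies, and a rule about each two visits is not an obvious way to express it.

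The 18–24 month consequence depends on reading a misprinted word as consecutive. That is correct, so it is a conditional consequence and not a proven wrong endpoint. Section II-6 also cites a published scan-measurement method, which might settle the pairing but is not available here.

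Derivation of change scores is often left to a statistical analysis plan, and none is shown. That would answer a complaint about silence. Here the protocol does state a rule, and the rule is unclear.

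Section 3 is loosely worded, since it asks about bioactivity at two years as well although that outcome stops at three months. This weakens it as an endpoint definition. It remains the only stated horizon for the question, and the scan schedule matches it.

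Interval wear is a legitimate measure. The protocol's own background describes a study that reported wear "during the T0-T6 and T6-T12 observation periods". The difficulty is only that increments, if that is what is meant, are not tied to the two-year question.

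A reader might also infer a particular loss of power from analysing a six-month increment. The documents give no scan error and tie the assumed effect size to no interval, so no such figure can be supported.

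**Conclusion.** The point holds as a defect in how the wear endpoint is fixed. T0 is not named as the reference scan anywhere in the protocol. On the most natural reading, the comparison at T4 covers 25% of follow-up and does not answer the research question. On a baseline-referenced reading it does, and the text does not choose between them. That 25% follows from the visit schedule and rests on reading the pairing rule as consecutive visits.

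No data are lost on any reading, because all five scans are taken and the T0–T4 loss can be obtained from them. The change should be made, and it is best made before any superimposition is analysed. It does not put the trial's data collection in doubt.

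**What to change.** In section II-6, replace the pairing rule with wording to this effect: *each follow-up scan (T1, T2, T3, T4) is superimposed on the T0 scan of the same tooth; wear at each time is the cumulative volume loss from T0.* Add that the T0–T4 loss is the comparison that answers the two-year question. In Table 3, remove the T0 cells or mark them as the reference. Losses over consecutive intervals may be kept as additional results.

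The cost is protocol wording. Scans and software stay the same, and the number of superimpositions equals that of the consecutive scheme. The downside is that interval wear becomes a derived or additional result. It can be obtained by subtracting cumulative losses at no extra work, or measured directly at the further workload shown above.

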#### **II-7- Assessment of the bioactivity:**

Bioactivity of each examined restoration will be determined by the evaluation of mineral density beneath the tested materials. Immediately after restoration (D0), an image plate digital sensor (Xios XG Supreme, Dentsply Sirona, UK) will be used for transmitting the radiographic

image of the selected tooth to the computer. A posterior parallel kit will be used for image standardization. Later, each restoration will be examined at standardized follow-up periods; one month (D1) and three months (D2) (Table 4 and 5). The image plate will be inserted at one end of the parallel kit, while the other end was connected to the x-ray cone. All the radiographs will be evaluated for the outcome by a software (ImageJ software, NIH, USA). The assessment of mineral density will be done by the software through performing the following measurements: in each image a line will be drawn along the CEJ to act as a reference, while another parallel line will be drawn at the bottom of the cavity. The distance between both lines will be standardized for each tooth by measuring the length of a vertical line connecting them. The length of the line centralized at the bottom of the cavity will be determined in pixels directly via the previously mentioned software. Such length will be fixed for each sample throughout assessment intervals. Three points on this line (at its start, middle and end) will be determined. The mineral density value at each of these points will be identified by taking the corresponding three readings from the software and recording them to calculate the average value. The mineral density mean value will be calculated from the software (Ibrahim et al, 2016).

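### The density line keeps a fixed pixel length over three exposures with no stated scaling or registration, which adds avoidable noise of unknown size to the bioactivity outcome

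*Protocol*

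**What the plan says.** All the relevant text is in Protocol section II-7, on the assessment of bioactivity. Each restored tooth is radiographed immediately after restoration (D0), at one month (D1) and at three months (D2).

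- **At exposure:** "A posterior parallel kit will be used for image standardization". The kit joins receptor and beam: "The image plate will be inserted at one end of the parallel kit, while the other end was connected to the x-ray cone".
- **On the image:** "in each image a line will be drawn along the CEJ to act as a reference", and a second, parallel line is placed at the cavity floor. For the gap between the two, "The distance between both lines will be standardized for each tooth by measuring the length of a vertical line connecting them".
- **The measurement line:** "The length of the line centralized at the bottom of the cavity will be determined in pixels directly via the previously mentioned software". The next sentence adds: "Such length will be fixed for each sample throughout assessment intervals".
- **The readings:** "Three points on this line (at its start, middle and end) will be determined", and the three values are averaged.

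The section describes no superimposition of the serial radiographs and no correction of pixel scale between visits. Section II-6, by contrast, superimposes the intraoral scans from different visits before wear volume is computed.

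**The concern.** A pixel count is not a physical length. The same number of pixels spans the same dentine at D0, D1 and D2 only if the projected scale is the same in all three images. The kit fixes the relation between beam and receptor within an exposure. The text does not say how the kit is brought back to the same seat on the tooth one and three months later. If the scale differs, a line of unchanged pixel length covers a slightly different stretch of dentine, and its ends fall on different tissue.

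Section 2 of the protocol names bioactivity, with wear resistance, as a primary objective. The outcome is an average of only three point readings, and section 6 plans 10 to 12 restorations per material. Each point carries one third of the result, so error in siting the points goes into every follow-up value and into any change from D0. With so few restorations, noise that software can remove cheaply should be removed.

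**Working it through.** The protocol gives no figure on this point to reproduce: no line length, pixel size, magnification tolerance or repeatability value. The check is therefore a geometric sensitivity calculation.

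**Inputs from the protocol (II-7):** three exposures; line length constant in pixels; line centred on the cavity floor; three points read (start, middle, end).

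**Inputs assumed:** line length L = 50 to 200 pixels; CEJ-to-floor distance H = 50 to 200 pixels; relative magnification change between exposures m = 1% to 10%.

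**Step 1. Effect of the fixed length.** At D0 the end of the line lies L/2 pixels from its centre. In a later image magnified by (1 + m), the same dentine lies (L/2)(1 + m) pixels from the centre, while the fixed line still ends at L/2.

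Miss at each end = (L/2) × m. Miss at the midpoint = 0, provided the line is re-centred correctly.

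| L (pixels) | m = 1% | m = 5% | m = 10% |
|---|---|---|---|
| 50 | 0.25 | 1.25 | 2.5 |
| 100 | 0.5 | 2.5 | 5 |
| 200 | 1 | 5 | 10 |

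For example, 100/2 × 0.05 = 2.5 pixels at each end.

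**Step 2. Effect of the CEJ-to-floor distance.** The text standardises this distance for each tooth but does not say in what unit it is carried from visit to visit. There are two readings.

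- *Held in pixels:* the whole line, midpoint included, moves vertically by H × m. The range is 50 × 0.01 = 0.5 pixel to 200 × 0.10 = 20 pixels; for H = 100 and m = 5% it is 5 pixels.
- *Line placed on the visible floor in each image:* this vertical shift largely disappears, and Step 1 is what remains, together with the error of siting by eye.

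**Step 3. From pixels to density.** The protocol gives neither the grey-level gradient near the cavity floor nor the error of repeat readings. A shift in pixels cannot be turned into density units, a standard deviation or a loss of power.

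**The case against.** The strongest reply is that II-7 does control geometry. The kit links plate and cone, the CEJ line is drawn in every image, the second line is parallel to it at the cavity floor, the distance between them is standardised per tooth, and the measurement line is centred. Together these amount to a manual alignment to landmarks. This stands. A reader might infer that the serial images have no alignment at all, and the text does not support that. What is absent is any stated rescaling or software registration. The CEJ line is also drawn afresh each time, so it carries its own placement error.

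A reader might also infer that the whole line is displaced by up to about 10 pixels. Assuming a CEJ-to-floor distance of 2 to 4 mm, a 1 to 5% magnification change and 0.02 to 0.03 mm per pixel, the shift is 2 × 0.01 = 0.02 mm to 4 × 0.05 = 0.20 mm, or 0.02/0.03 = 0.67 pixel to 0.20/0.02 = 10 pixels. That holds only if the CEJ-to-floor distance is carried over in pixels, which the protocol does not say. The quantity it does fix in pixels is the line length, and this leaves the midpoint in place.

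A third inference is bias between materials. Table 1 lists different fillers for the two composites, so a point drifting onto the restoration might read differently in each. The protocol gives no radiopacity figures. Both materials are imaged and read by the same procedure in the same patients, with the molar allocated at random. Bias is conceivable but not shown. Spurious gain or loss in a single tooth is not the planned inference either, because the statistical analysis section compares groups at each time.

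Finally, II-7 cites a published method that is not available here, and registration detail could sit in an imaging procedure. Silence alone would be weak ground. The fixed pixel length, however, is a stated rule, and the criticism rests on that.

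**Conclusion.** The point holds in a limited form. Fixing the line length in pixels over D0, D1 and D2, with no stated scaling or registration, allows a change in magnification or seating to shift two of the three reading points. If the CEJ-to-floor distance is also held in pixels, it shifts all three. Under the assumed ranges each end moves between 0.25 and 10 pixels, and 2.5 pixels in the middle case of a 100-pixel line and a 5% change. These figures illustrate the mechanism; they do not estimate this trial's error, whose true size cannot be obtained from the protocol.

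The consequence that can be supported is avoidable noise in the follow-up densities and in their change from D0. Nothing in the document shows that it favours either composite. This is a cheap gain in precision for a primary objective, not a flaw that invalidates the comparison.

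**What to change.** In II-7, replace the fixed pixel length by one of two rules.

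1. **Preferred.** In ImageJ, register each tooth's D1 and D2 images to its D0 image on landmarks that should not change (CEJ points, root outline, restoration outline). Then transfer the D0 line coordinates to the registered images instead of redrawing the line. State beforehand the landmark misfit above which registration is repeated.
2. **Minimum.** Scale the line length in each image to a fixed anatomical distance on that tooth. If the reference distance measures 100 pixels at D0 and 105 at D1, a 100-pixel line becomes 105 pixels and the 2.5-pixel miss at each end is removed.

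Under the second rule, also state that the CEJ-to-floor distance is scaled in the same way and not carried over in pixels.

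The cost is a few minutes per image for 24 teeth × 2 follow-up images = 48 images, in software the protocol already names, with no extra exposure or visit. There are two drawbacks: resampling smooths the grey values slightly, and two-dimensional registration does not correct a changed projection angle, so the parallel kit is still needed.
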